## 2.2.3 Ongoing Clinical Studies

### MK-2060-007:

MK-2060-007 is an event driven, randomized, placebo-controlled, parallel-group, multi-site, double-blind study of MK-2060 in participants with ESKD receiving hemodialysis via an AVG. This Phase 2 study is designed to evaluate the efficacy and safety of MK-2060 20 mg QW and MK-2060 6 mg QW (with 3 loading doses in Week 1). As of 10-Sep-2023, 506 participants have been randomized in MK-2060-007 and 502 have been dosed with a maximum exposure of 687 days. MK-2060-007 is ongoing and safety data are blinded and preliminary.

#### MK-2060-009:

This is a Phase 1 randomized, placebo-controlled, single-ascending dose clinical study to evaluate the safety, PK, and pharmacodynamics of IV MK-2060 in healthy Chinese male adult participants. As of 10-Sep-2023, 3 panels of 12 participants each (9 MK-2060: 3 placebo) were administered single 8 mg, 20 mg, and 40 mg IV doses of MK-2060 or placebo (9:3). Twenty-four (24) participants in Panel A-B have completed their last visit and all assessments. The estimated LPLV is 28-Oct-2023.

#### MK-2060-012:

This is a Phase 1 randomized, placebo-controlled single-dose clinical study to evaluate the safety, tolerability, PK, and pharmacodynamics of IV MK-2060 in Japanese older participants with end-stage kidney disease on dialysis. As of 10-Sep-2023, 17participants were administered a single 50 mg IV dose of MK or placebo (3:1 ratio). LPI was achieved with estimated LPLV 07-Feb-2024.

#### MK-2060-013

This is a randomized, placebo-controlled, single-ascending dose clinical study to evaluate safety, tolerability, PK and pharmacodynamics of MK-2060 in healthy Japanese adult participants. As of 10-Sep-2023, 4 panels of 12 participants each (3:1 ratio) were administered single 8 mg, 20 mg, and 50 mg IV doses of MK-2060, and 30 mg SC dose of MK-2060, or placebo (3:1 ratio). LPLV: is estimated 18-Dec-2023

#### 2.3 Benefit/Risk Assessment

Participants in clinical studies will not receive direct benefit from treatment during participation as clinical studies are designed to provide information about the safety and properties of an investigational medicine.

Additional details regarding specific benefits and risks for participants participating in this clinical study may be found in the accompanying IB and informed consent documents.

## 3 HYPOTHESES, OBJECTIVES, AND ENDPOINTS

Hypotheses are aligned with objectives in the Objectives and Endpoints table.

This study is to be conducted in adult participants with chronic and/or end-stage kidney disease.

Primary Objectives	Primary Endpoints
Part 1: To evaluate the safety and tolerability of MK-2060 following singledose SC administration in adult participants with Stage 4 or 5 Chronic Kidney Disease.  Part 2: To evaluate the safety and tolerability of MK-2060 following multipledose SC administration in adult participants with Stage 4 or 5 Chronic Kidney Disease.	Bleeding related AEs, AEs, and discontinuations due to AEs
Part 3: To evaluate the safety and tolerability of MK-2060 following single-dose SC administration in adult participants with End-Stage Kidney Disease on Peritoneal Dialysis.	
Part 1: To evaluate plasma pharmacokinetics of MK-2060 following single-dose SC administration in adult participants with Stage 4 or 5 Chronic Kidney Disease.	Measurement of MK-2060 plasma AUC0- ∞, AUC0-168, Cmax, C168, Tmax, terminal t1/2, CL/F and Vz/F
Hypothesis: The true geometric mean of AUC0-∞ after a single well tolerated dose of MK-2060 in adult participants with Stage 4 or 5 Chronic Kidney Disease is at least 11300 nM*hr.	
Part 2: To evaluate plasma pharmacokinetics of MK-2060 following multiple-dose SC administration in adult participants with Stage 4 or 5 Chronic Kidney Disease.  Estimation: The effect of multiple-dose SC administration of MK-2060 in adult participants with Stage 4 or 5 Chronic Kidney Disease will be estimated.	

Part 3: To evaluate plasma pharmacokinetics of MK-2060 following single-dose SC administration in adult participants with End-Stage Kidney Disease on Peritoneal Dialysis.  Estimation: The effect of single-dose SC administration of MK-2060 in adult participants with End Stage Kidney Disease on Peritoneal Dialysis will be estimated.	
Secondary Objective	Secondary Endpoint
Part 1: To evaluate the effect of MK-2060 on aPTT following single dose SC administration in adult participants with Stage 4 or 5 Chronic Kidney Disease.  Part 2: To evaluate the effect of MK-2060 on aPTT following multiple-dose SC administration in adult participants with Stage 4 or 5 Chronic Kidney Disease.  Part 3: To evaluate the effect of MK-2060 on aPTT following single dose SC administration in adult participants with End-Stage Kidney Disease on Peritoneal Dialysis.	aPTT fold change from baseline
Tertiary/Exploratory Objectives	Tertiary/Exploratory Endpoints
Parts 1 and 3: To explore the effect of MK-2060 on Factor XI (FXI) activity levels following a single SC dose.  Part 2: To explore the effect of MK-2060 on Factor XI (FXI) activity levels following multiple SC doses.	FXI activity level fold change from baseline
Parts 1 and 3: To explore the effect of MK-2060 on prothrombin time (PT) following a single SC dose.	PT fold change from baseline
Part 2: To explore the effect of MK-2060 on prothrombin time (PT) following multiple SC doses.	

To explore the relationship between genetic variation and response to the treatment(s) administered, and mechanisms of disease. Variation across the human genome may be analyzed for association with clinical data collected in this study.	Germline genetic variation and association to clinical data collected in this study
To explore the development and impact of ADAs measured in blood samples after single and multiple SC doses of MK-2060 is administered in adult participants with Chronic and/or End-Stage Kidney Disease.	ADAs

#### 4 STUDY DESIGN

## 4.1 Overall Design

This is a 3-part, multi-site, randomized, double-blind, placebo-controlled, single-dose and multiple-dose study to assess the safety, tolerability, PK and pharmacodynamics of SC MK-2060 in participants with CKD4, CKD5, and ESKD on Peritoneal Dialysis.

In Part 1, participants with CKD4 or CKD5 (eGFR from 10 to 29) (n=12) will be randomized in a 3:1 ratio to receive a single 30-mg SC dose of MK-2060 (n=9) or placebo (n=3).

In Part 2, participants with CKD4 or CKD5 (n= 12) will be randomized in a 3:1 ratio to receive 4 loading doses of 30 mg SC MK-2060 or placebo (given daily for 4 days) followed by 30 mg SC MK-2060 (n=9) or placebo (n=3) every week for 3 additional weeks. A minimum of 4 participants with CKD5 will be enrolled in the study, of which a minimum of 3 will receive MK-2060.

Participants who successfully completed Part 1 through the post study visit may enroll in Part 2 provided screening criteria are met.

In Part 3, an open label study, participants with ESKD who are on peritoneal dialysis will receive a single 30 mg SC dose of MK-2060 (n=9).

In all 3 parts, participants will be closely monitored for safety and tolerability, including safety labs, local lab aPTT and PT results, physical exam to check incidence of bleeding, VS and 12-lead ECG, as well as local injection site reactions and for systemic reactions.

The study design is depicted in Figure 1, Figure 2, and Figure 3. Part 2 and Part 3 can be completed in parallel. For all participants, blood samples will be collected for MK-2060 plasma PK and pharmacodynamics. The precise timing of safety and tolerability measurements, PK and pharmacodynamics samples may be altered during the course of the study based on newly available data.

Because this is a Phase 1 assessment of MK-2060 in humans, the PK, pharmacodynamic, and safety profiles of the compound are still being elucidated. This protocol is therefore written with flexibility to accommodate the inherent dynamic nature of Phase 1 clinical studies. Refer to Section 8.11.7 for examples of modifications permitted within the protocol parameters.

Specific procedures to be performed during the study, including prescribed times and associated visit windows, are outlined in Section 1.3 of the SoA. Details of each procedure are provided in Section 8.

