Informed Consent	X																					Sec. 5.1, 8.1.1.1
Informed Consent for FBR	X																					Sec. 5.1, 8.1.1.2
Inclusion/Exclusion Criteria	X	X	X																			Sec. 5.1, 5.2, 8.1.2
Participant ID Card	X																					Sec. 8.1.3
Participant ID Bracelet			X																			Sec. 8.11.2
Medical History	X	X	X																			Sec. 8.1.4
Assignment of Screening Number	X																					Sec. 8.1.6
Assignment of Randomization Number			X																			The randomization number is assigned at the time of study drug administration. Sec. 5.5, 8.1.7

												Part 2	2									
	≤28	eening 8 days Day 1								Int	erve	ntion	1								Post- study	Notes
Scheduled Timing (Week)	Screening 1	Screening 2 a		We	ek 1		We 2		We 3		W	∕eek ∙	4			Pos	st W	'eek	4			
Scheduled Timing (Day)			1	2	3	4	8	10	15	17	22	23	26	29	35	42	49	63	81	111	130	
Visit Window (Day)			NA	NA	NA	NA	NA	±1	NA	±1	NA	NA	±1	NA	±2	±2	±2	±2	±3	±3	±7	
Prior/Concomitant Medication Review	X																				X	Sec. 5.2, 6.5, 8.1.5
Safety/Clinic Procedures																						
Full physical examination	X		X				X		X		X			X							X	Sec. 8.3.1, 8.3.7
Targeted physical examination				X	X										X		X	X	X			Sec. 8.3.1, Sec. 8.3.7
Height	X																					Sec. 8.3.1
Weight	X																				X	BMI to be taken only at Screening 1. Sec. 8.3.1
Orthostatic VS (HR, BP)	X		X			X	X		X		X											Days 1, 4, 8, 15 and 22 measurements will be predose; Sec. 8.3.2.2.
Semi-recumbent VS (HR, BP)	X	X	X			X	X		X		X		X	X		X		X			X	Days 1, 4, 8, 15 and 22 measurements will be predose; Sec. 8.3.2
RR and body temperature	X		X			X	X		X		X											Days 1, 4, 8, 15 and 22 measurements will be predose; Sec. 8.3.2.

												Part 2	2									
	≤28	eening 8 days Day 1								Int	erve	ntion	ļ								Post- study	Notes
Scheduled Timing (Week)	Screening 1	Screening 2 a		We	ek 1		We 2		We 3		W	√eek 4	4			Pos	t W	eek	4			
Scheduled Timing (Day)			1	2	3	4	8	10	15	17	22	23	26	29	35	42	49	63	81	111	130	
Visit Window (Day)			NA	NA	NA	NA	NA	±1	NA	±1	NA	NA	±1	NA	±2	±2	±2	±2	±3	±3	±7	
12-lead ECG	X		X			X	X		X		X			X							X	Days 1, 4, 8, 15 and 22 measurements will be predose; Sec. 8.3.3.
Domiciling			X	X	X	X	X		X		X											Sec. 8.1.11.
Standard Meals			X				X		X		X											Sec. 5.3.1.

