## 6.3 Measures to Minimize Bias: Randomization and Blinding

## **6.3.1** Intervention Assignment

Participants will be assigned randomly according to a computer-generated allocation schedule. Sample allocation schedules are shown below in Table 2, Table 3, and Table 4.

Table 2 Sample Allocation Schedule for Part 1

Treatment Group	Participants	Dose
1	n=9	MK-2060 30 mg SC
2	n=3	Placebo

n=number of participants; SC=subcutaneous

Table 3 Sample Allocation Schedule for Part 2

Treatment Group	Participants a	Dose
1	n=9	MK-2060 30 mg SC
2	n=3	Placebo

a. To ensure a minimum of 3 CDK4 and CKD5 participants receive MK-2060, assignment of randomization numbers for CKD4 participants will occur in ascending order (starting block). Assignment of randomization number for CKD5 participants will occur in descending order (ending block).

n=number of participants; SC=subcutaneous

Table 4 Sample Allocation Schedule for Part 3

Treatment Group	Participants	Dose
1	n=9	MK-2060 30 mg SC

n=number of participants; SC=subcutaneous

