## 6.8 Clinical Supplies Disclosure

The emergency unblinding call center will use the intervention randomization schedule for the study to unblind participants and to unmask study intervention identity for this study. The emergency unblinding call center should only be used in cases of emergency (see Section 8.1.10). The Sponsor will not provide random code/disclosure envelopes or lists with the clinical supplies.

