## 8.1.3 Participant Identification Card

All participants will be given a participant identification card identifying them as participants in a research study. The card will contain study-site contact information (including direct telephone numbers) to be used in the event of an emergency. The investigator or qualified designee will provide the participant with a participant identification card immediately after

the participant provides documented informed consent. At the time of intervention randomization, site personnel will add the treatment/randomization number to the participant identification card.

The participant identification card also contains contact information for the emergency unblinding call center so that a health care provider can obtain information about study intervention in emergency situations where the investigator is not available.

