#### 8.1.7 Assignment of Treatment/Randomization Number

For Parts 1 and 2, all eligible participants will be randomly allocated and will receive a treatment/randomization number. For Part 3, all eligible participants will be allocated, by nonrandom assignment, and will receive a treatment/allocation number. The treatment/randomization/allocation number identifies the participant for all procedures occurring after treatment randomization/allocation. Once a treatment/randomization/allocation number is assigned to a participant, it can never be reassigned to another participant.

A single participant cannot be assigned more than 1 treatment/randomization/allocation number.

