#### **8.11.2** Treatment Period

Refer to the Schedule of Activities (Section 1.3) and Administrative and General Procedures (Section 8.1).

After all predose procedures have been completed and it is confirmed that the participant meets eligibility; the participant will be given a participant ID bracelet and assigned a unique randomization number associated with a specific treatment as defined by a computer-generated randomization schedule. Participants will report to the CRU prior to the scheduled day of dosing or time specified by the investigator. On the day of dosing, participants will fast from all food and drinks, except water, for at least 8 hours prior to until 2-hours poststudy drug administration when they will be given a light breakfast (see Section 5.3.1). Participants will be administered study intervention as indicated in Section 6. Participants who, on Day 1, have a significant acute illness or fever prior to the administration of study drug may be rescheduled.

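### Does the one-number-per-participant rule in Section 8.1.7 stop Part 1 completers from being randomized in Part 2?

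*Combined protocol and SAP*

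**What the plan says.** Section 4.1 describes Parts 1 and 2 as separate randomized panels of 12, each 3:1 (9 MK-2060, 3 placebo), and then adds: "Participants who successfully completed Part 1 through the post study visit may enroll in Part 2 provided screening criteria are met".

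Section 8.1.7 sets the numbering rules. It begins: "For Parts 1 and 2, all eligible participants will be randomly allocated and will receive a treatment/randomization number". It ends: "A single participant cannot be assigned more than 1 treatment/randomization/allocation number". Section 8.1.6 has a parallel limit of one screening number per participant.

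The number carries the treatment. Under Section 8.11.2 an eligible participant is "assigned a unique randomization number associated with a specific treatment as defined by a computer-generated randomization schedule". The Part 2 Schedule of Activities places the assignment on Day 1 and notes: "The randomization number is assigned at the time of study drug administration".

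Section 6.3.1 gives Part 2 its own allocation schedule (Table 3). Its footnote has CKD4 participants take numbers from the low end upward. For CKD5 it says: "Assignment of randomization number for CKD5 participants will occur in descending order (ending block". The aim is at least 3 participants of each stage on MK-2060.

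On unblinding, Section 6.8 says: "The emergency unblinding call center will use the intervention randomization schedule for the study to unblind participants". Section 8.1.3 says: "At the time of intervention randomization, site personnel will add the treatment/randomization number to the participant identification card".

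**The concern.** Taken at face value, two rules cannot both be obeyed for the same person. Someone who finished Part 1 already holds a number tied to a Part 1 treatment. To join Part 2 that person must be randomized again, from a different list, and the last sentence of Section 8.1.7 appears to forbid a second number. The rule is not simply old boilerplate: the current text names all three parts and still states the limit per participant rather than per part.

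Two consequences might follow. A site might treat the Part 2 route as closed. Or it might carry the Part 1 number forward, leaving the participant outside the Table 3 schedule and outside the mechanism that secures the CKD4 and CKD5 minimums. In the second case the number on the identification card would point to the Part 1 assignment during a seven-dose regimen, and an emergency unblinding could return the wrong arm.

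**Working it through.** **Count of numbers.** The inputs are Part 1 n = 12 and Part 2 n = 12 (Section 4.1), one number per randomized place (Section 8.1.7, first sentence, read per part) and one number per person (Section 8.1.7, last sentence). Let k be the number of rollovers.

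- Numbers needed in Parts 1 and 2: 12 + 12 = 24.
- Distinct people, and so numbers permitted: 24 − k.
- Shortfall: 24 − (24 − k) = k.

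This gives 0 for k = 0, 1 for k = 1 and 12 for k = 12. It only restates that each rollover needs one extra number. Each rollover is 1/12 = 8.3% of Part 2 allocations, which measures share and not bias or loss of precision.

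**Range of k.** The documents give no expected figure. The route is optional, so the lower limit is 0. The ceiling of 12 is the size of Part 1 and ignores eligibility. A rollover must meet the screening criteria again, including the renal function range and stability rules. Exclusion 17 also bars a monoclonal antibody within 3 months or 5 half-lives, whichever is longer, and MK-2060 is a monoclonal antibody. The half-life is redacted, so a realistic k cannot be derived.

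**What the provisions tell a site to do with a rollover.**

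| Provision | Instruction for a Part 2 entrant |
|---|---|
| Section 4.1 | Randomized 3:1 within Part 2 |
| Part 2 Schedule of Activities | Card at Screening 1; number and bracelet on Day 1 |
| Table 3, footnote a | Number taken from the Part 2 schedule, from the end that matches CKD stage |
| Section 8.1.7, last sentence | No more than one number per participant |

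Three of the four point to a fresh Part 2 number. None describes carrying a Part 1 number forward. Section 8.1.7 deals with allocation part by part, so reading its limit within each part is possible and removes the conflict, although the sentence does not say so.

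**Effect on the Part 1 test.** A rollover must first complete the Part 1 poststudy visit (Day 90). That is the last scheduled Part 1 sample for plasma MK-2060, so the data behind AUC0-∞ are complete before any Part 2 number is drawn. The posterior probability in Section 9.6 does not depend on k.

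**Effect on Part 2.** Section 9.6 limits Part 2 to descriptive statistics. Section 9.5 analyzes participants by the treatment they actually received. A rollover who draws from Table 3 contributes to the arm received, whatever label the number carries.

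**Effect on unblinding.** An error requires reuse of the Part 1 number. If that happened, and if the two parts were independent 3:1 draws, the two arms would differ with probability 2 × 0.75 × 0.25 = 37.5%. Under the Part 2 Schedule of Activities the card step is repeated at Screening 1, and Section 8.1.3 has the number added at randomization. The card would then show the Part 2 number.

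**The case for a change.** The strongest case for a change is that the text means what it says. The limit applies to a single participant without qualification, and Section 4.1 plainly regards the rollover as the same participant. Rescreening under Section 8.11.1 says nothing about a second randomization number, and the modifications allowed by Section 8.11.7 do not cover numbering. A site must therefore either breach Section 8.1.7 or refuse a route that Section 4.1 grants. One or two sentences would cure it, without new visits, samples or analyses.

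Much of this stands. No exception is written, Section 8.1.6 has the same gap for screening numbers, and a clarifying line would be harmless. What does not stand is the step from a numbering conflict to invalid randomization. Validity depends on a chance draw from the Part 2 list, which the other provisions require. A second number breaches a bookkeeping sentence and leaves that draw intact. The unblinding scenario rests on a workaround that no section describes and that the Part 2 Schedule of Activities leads away from. If the opposite happens and rollovers are turned away, Part 2 enrolls other eligible participants and its descriptive results are equally sound.

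**Conclusion.** The conflict between Sections 4.1 and 8.1.7 is a genuine drafting slip, and it calls for no change to the plan. Its size is one number per rollover, with k unknown and possibly zero. It has no effect on the Part 1 hypothesis test, on the descriptive Part 2 results or on any documented safety outcome. This rests on one assumption: that sites follow the Part 2 Schedule of Activities and Table 3 and issue a Part 2 number, or else do not enroll the person. The sponsor has used protocol clarification letters for wording of this kind and could do so here if a rollover arises. Whether earlier MK-2060 exposure should be marked in the Part 2 listings is a separate question that the numbering rule does not decide.

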### 4.2 Scientific Rationale for Study Design

To date, the safety and tolerability of MK-2060 have been evaluated in healthy participants dosed both via SC and IV administration (P001), and in ESKD-HD participants with IV dosing (P004 and P008). Ongoing Phase 1 studies are assessing safety and tolerability of IV

doses of MK-2060 in healthy Chinese and Japanese participants (P009 and P013), IV doses in Japanese dialysis patients (P012), and SC doses in healthy Japanese participants (P013). An ongoing Phase 2b study (P007) is evaluating the safety and efficacy of MK-2060 in ESKD-HD patients using IV dosing. The highest IV dose tested in the Phase 2b study is 20 mg IV. Because severe CKD patients not yet on dialysis (ie, CKD4, CKD5) may also derive a benefit from inhibition of FXI, enrollment of these patients in a Phase 3 study is warranted. In Phase 3, MK-2060 will be dosed IV in ESKD-HD patients due to the simplicity of IV administration during hemodialysis sessions. However, dosing in CKD4 and CKD5 patients not yet on dialysis will require SC administration, and SC PK has not yet been characterized in these patients. For patients with ESKD on peritoneal dialysis, IV administration is not practical, and enrollment of this patient population in Phase 3 requires an assessment of safety and PK of SC doses of MK-2060 in ESKD. Globally, approximately 11% of ESKD patients use peritoneal dialysis, with higher rates of utilization in some regions and therefore it is important to include this population so that they can also be candidates for MK-2060 therapy. Therefore, the purpose of this study is to characterize the SC PK of MK-2060 in CKD4, CKD5, and ESKD-Peritoneal Dialysis patients using single and multiple doses, in order to help provide information to guide dose selection for future clinical studies. Part 1 of this study will test the hypothesis that a single 30 mg SC dose of MK-2060 in CKD4 patients will achieve exposures such that if multiple doses were given and steady state exposures were achieved, our pharmacodynamics target would be projected to be achieved, within the predicted degree of

